2.5.2 Data handling conventions for secondary efficacy variables

2.5.3 Missing data

For categorical variables, patients with missing data are not included in calculations of percentages unless otherwise specified. When relevant, the number of patients with missing data is presented.

Handling of computation of treatment duration if investigational medicinal product end of treatment date is missing

For the calculation of the treatment duration, the date of the last dose of IMP is equal to the date of last administration reported on the treatment status e-CRF page. If this date is missing, the exposure duration should be left as missing.

The last dose intake should be clearly identified in the e-CRF and should not be approximated by the last returned package date.

Handling of medication missing/partial dates

No imputation of medication start/end dates or times will be performed. If a medication date or time is missing or partially missing and it cannot be determined whether it was taken prior or concomitantly, it will be considered a prior, concomitant, and post-treatment medication.

Handling of adverse events with missing or partial date/time of onset

Missing or partial adverse event onset dates and times will be imputed so that if the partial adverse event onset date/time information does not indicate that the adverse event started prior to treatment or after the treatment-emergent adverse event period, the adverse event will be classified as treatment-emergent. No imputation of adverse event end dates/times will be performed. These data imputations are for categorization purpose only and will not be used in listings. No imputation is planned for date/time of adverse event resolution.

Handling of adverse events when date and time of first investigational medicinal product administration is missing

When the date and time of the first IMP administration is missing, all adverse events that occurred on or after the day of randomization should be considered as treatment-emergent adverse events. The exposure duration should be kept as missing.

The last dose intake should be clearly identified in the e-CRF and should not be approximated by the last returned package date.

Handling of missing assessment of relationship of adverse events to investigational medicinal product

If the assessment of the relationship to IMP is missing, then the relationship to IMP has to be assumed and the adverse event considered as such in the frequency tables of possibly related adverse events, but no imputation should be done at the data level.

Handling of missing severity of adverse events

If the severity is missing for 1 of the treatment-emergent occurrences of an adverse event, the maximal severity on the remaining occurrences will be considered. If the severity is missing for all the occurrences, a “missing” category will be added in the summary table.

Handling of potentially clinically significant abnormalities

If a patient has a missing baseline he will be grouped in the category “normal/missing at baseline.”

For PCSAs with 2 conditions, one based on a change from baseline value or a normal range and the other on a threshold value, with the first condition being missing, the PCSA will be based only on the second condition.

For a PCSA defined on a threshold and/or a normal range, this PCSA will be derived using this threshold if the normal range is missing; e.g., for eosinophils the PCSA is > 0.5 GIGA/L or $> \text{ULN}$ if $\text{ULN} \geq 0.5$ GIGA/L. When ULN is missing, the value 0.5 should be used.

Measurements flagged as invalid by the laboratory will not be summarized or taken into account in the computation of PCSA values.

2.5.4 Windows for time points

Time windows are used to assigned protocol planned time points based on the actual timing of the considered assessment rather than based on the theoretical timing of the visit it comes from.

The **actual hour** of an assessment (scheduled or unscheduled) for which the date and time are available is calculated in hours or days from the date and time of IP start as: *date&time of assessment minus date&time of IMP start*.

While the **actual day** of an assessment for which only the date is available (no time) is calculated in days from the date of IP start as: *date of assessment minus date of IMP start*.

Handlings of assessments performed outside defined time windows will depend on the analyses and are detailed in dedicated sections, as well as handling of several assessments performed within the same time window.

In the case where more than one assessment of a parameter falls within the same time window, only the assessment closest to the targeted time point will be used. In cases where two assessments are equally close to the targeted time point, the first assessment will be used.

2.5.4.1 **Time windows for efficacy evaluation**

Before Day 4, time points assigned to scheduled or unscheduled parasitemia and to concomitant - i.e. coming from the same visit - body temperature will be based on the actual hour of the blood thick film and allowed time windows, as specified in Table 3. In case, the blood thick film is missing at a visit, but body temperature assessment is available (or if missing), then the theoretical time point of the visit will be assigned because only the date (no time) of assessment is collected for body temperature.

Table 3 – Time windows definition before Day 4

Protocol planned time point	Allowed deviation from targeted time	Corresponding window of time for actual blood film timing
Hour 6	-1/+2 hours (included)	5 hours to 8 hours
Hour 12	-1/+2 hours (included)	11 hours to 14 hours
Hour 18	-1/+2 hours (included)	17 hours to 20 hours
Hour 24 (Day 1)	-1/+2 hours (included)	23 hours to 26 hours
Hour 30	-1/+2 hours (included)	29 hours to 32 hours
Hour 36	-2/+3 hour (included)	34 hours to 39 hours
Hour 48 (Day 2)	±3 hours (included)	45 hours to 51 hours
Hour 72 (Day 3)	±4 hours (included)	68 hours to 76 hours

Note: bold font is used when the time point is involved in the ACPR definition.

From Day 4, time points assigned to scheduled or unscheduled parasitemia, body temperature will be based on the actual day of assessment and allowed time windows, as specified in Table 4.

Table 4 – Time windows definition from Day 4

Protocol planned time point	Allowed deviation from targeted time	Corresponding window of time for actual blood film timing
Hour 96 (Day 4)	0	Day 4
Hour 120 (Day 5)	0	Day 5
Hour 144 (Day 6)	0	Day 6
Hour 168 (Day 7)	0	Day 7

Day 10	±1 days (included)	9 days to less than 11 days
Day 14	±1 days (included)	12 days to less than 15 days
Day 21	±2 days (included)	19 days to less than 23 days
Day 28	±2 days (included)	26 days to 30 days

2.5.4.2 Time windows for safety evaluation

2.5.4.2.1 Time windows for laboratory evaluation

Visit	Time window for the actual laboratory assessment timing
Baseline	Before IP start
Hour 48 (Day 2)	36 hours to less than 48 hours
Hour 72 (Day 3)	48 hours to less than 84 hours
Hour 96 (Day 4)	84 hours to less than 5 days
Hour 168 (Day 7)	5 days to less than 11 days
Day 14	11 days to less than 18 days
Day 21	18 days to less than 25 days
Day 28	25 days to less than 32 days

2.5.4.2.2 Time windows for vital signs evaluation

Only the date (no time) of assessment is collected for vital signs, therefore, time windows are only defined for actual timing greater or equal to 4 days. For lower timings, the eCRF visit will be used. In particular, baseline will be V1 assessments.

Visit	Time window for the actual vital sign assessment timing
Hour 168 (Day 7)	4 days to less than 9 days
Day 10	9 days to less than 12 days
Day 14	12 days to less than 18 days
Day 21	18 days to less than 25 days
Day 28	25 days to less than 35 days

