2.1.5.4 Vital signs variables

Vital signs include heart rate, systolic and diastolic blood pressure (SBP and DBP), temperature and weight. At each visit where blood pressure is scheduled i.e. Visit 1 (Screening/Pre-dose), Visit 2 [hour 6 and 12), Visit 3 (hour 24), Visit 4 (hour 48), Visit 5 (hour 72) only if patient still hospitalized, Visit 6 (hour 96) only if patient still hospitalized, Visit 8 (hour 144), Visit 9 (hour 168), Visit 10 (Day 10), Visit 11 (Day 14), Visit 12 (Day 21) and Visit 13 (Day 28), three assessments, at least 1 minute apart, will be performed and recorded on the e-CRF as the average of the 3 blood pressure readings according to procedures described in the protocol according to supine position.

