2.4.5.4 Analyses of vital sign variables

The summary statistics (including number, mean, median, standard deviation, minimum and maximum) of all vital signs variables (raw data and changes from baseline) will be calculated for each visit or study assessment (baseline, each post-baseline time point, worst on-treatment value) by treatment group.

The incidence of PCSAs at any time during the on-treatment period will be summarized by treatment group irrespective of the baseline level and/or according to the following baseline status categories:

- Normal/missing
- Abnormal according to PCSA criterion or criteria

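### The vital-sign windows have no row for Hour 144 or Hour 96 and assign both to Hour 168, so the by-visit vital-sign summaries omit these assessments or show them as Day 7

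*SAP*

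**What the plan says.** SAP section 2.1.5.4 lists the visits at which vital signs are taken. Between Day 4 and Day 7 these are "Visit 6 (hour 96) only if patient still hospitalized, Visit 8 (hour 144), Visit 9 (hour 168"). The last two carry no condition.

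SAP section 2.4.5.4 states that summary statistics for values and changes from baseline "will be calculated for each visit or study assessment", and names each post-baseline time point among them.

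SAP section 2.5.4.2.2 explains that only the date of a vital-sign assessment is collected, and so "time windows are only defined for actual timing greater or equal to 4 days". It adds: "For lower timings, the eCRF visit will be used". The first row of its table is Hour 168 (Day 7), with the window "4 days to less than 9 days". The remaining rows are Days 10, 14, 21 and 28.

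SAP section 2.5.4 defines the actual day, where no time is recorded, as "date of assessment minus date of IMP start". When several records fall in one window, "only the assessment closest to the targeted time point will be used", and a tie goes to the earlier record. SAP section 2.5.5 sends all visits through this re-allocation before the by-visit summaries are made.

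**The concern.** The schedule has three assessments between Day 4 and Day 8, and the window table has one place to put them. The eCRF visit label cannot rescue Hour 96 or Hour 144, because it is kept only below Day 4. Two results follow for the by-visit tables. A promised time point, Hour 144, has no row. And the Hour 168 row can hold a measurement taken on another scheduled visit, with nothing in the table to show it. What is at stake is the correct description of pulse, blood pressure and temperature as safety variables over the first week, including in patients kept in hospital to Day 4.

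**Working it through.** The plan states no figure to reproduce, so the check is to apply its rules to its own schedule.

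**Inputs.** Scheduled days are Day 4 (Hour 96), Day 6 (Hour 144) and Day 7 (Hour 168), from SAP 2.1.5.4. The only window reaching them is 4 ≤ day < 9 with target Day 7, from SAP 2.5.4.2.2. The selection rule is the smallest |day − 7|, with ties to the earlier record, from SAP 2.5.4.

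**Assignment.** Days 4, 6 and 7 all satisfy 4 ≤ day < 9, so all three are labelled Hour 168.

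**Selection.**

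| Records available | Distance from Day 7 | Shown as Hour 168 | Not shown by visit |
|---|---|---|---|
| Days 4, 6, 7 | 3, 1, 0 | Day 7 | Days 4 and 6 |
| Days 6, 7 | 1, 0 | Day 7 | Day 6 |
| Days 4, 6 (Day 7 missed) | 3, 1 | Day 6 | Day 4 |
| Day 4 only | 3 | Day 4 | none |
| Visit 8 on Day 6, Visit 9 on Day 8 | 1, 1 (tie) | Visit 8 | Visit 9 |
| Visit 8 on Day 7, Visit 9 on Day 8 | 0, 1 | Visit 8 | Visit 9 |

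In no case is a record labelled Hour 144. In the last two rows the real Visit 9 is the record left out.

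**Size.** The unconditional post-dose time points are Hours 6, 12, 24, 48, 144 and 168 and Days 10, 14, 21 and 28, which makes ten. One of the ten has no row. With 35 patients planned in each of four arms, 4 × 35 = 140, so at most about 140 Hour 144 records are left out or relabelled. To these are added the Hour 96 records dated Day 4 or later. Their number depends on how many patients stay in hospital, which the documents do not predict.

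**Comparison with the other tables.** The laboratory and ECG tables (SAP 2.5.4.2.1 and 2.5.4.2.3) each give Hour 96 its own row. Efficacy Table 4 (SAP 2.5.4.1) has separate rows for Days 4, 5, 6 and 7 based on the actual day, so date-only recording does not rule out such rows.

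**The case against.** The best defence is that the wide row is deliberate. Only dates are collected, the rows run without a gap from Day 4 to before Day 35, and the time points in SAP 2.4.5.4 could be read as those that the window table defines. This does not succeed. SAP 2.5.4 selects one record and does not pool, and nothing states that Hours 96 and 144 are merged with Hour 168. Date-only recording explains the lack of hourly windows before Day 4, but not the lack of whole-day rows afterwards. The treatment is also uneven: Hour 72, which has the same in-hospital condition, keeps its eCRF label, while Hour 96 loses it.

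Other parts of the defence stand. A reader might infer that Day 4 and Day 6 vital signs are discarded from the safety analysis, or that abnormal values in patients kept in hospital would be missed. The documents do not support that. SAP 2.4.5 bases PCSA counts on every on-treatment evaluation, SAP 2.4.5.4 summarises the worst on-treatment value separately, and temperature used for efficacy follows Table 4.

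A reader might also infer that Hour 168 is routinely filled with data three days early. That needs a Day 4 record and no nearer one. In the usual case the shift is one day, and it requires a missed or late Visit 9.

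Finally, 140 is a ceiling. It assumes that every randomised patient has a Day 6 record, whereas protocol section 10.1 anticipates around 15% early dropout.

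**Conclusion.** The concern holds, within limits. Under the rules as written, the by-visit values and changes from baseline planned in SAP 2.4.5.4 cannot be produced for Hour 144, nor for Hour 96 records dated Day 4 or later. The Hour 168 row may contain Day 6 or Day 4 data, and it can exclude a Visit 9 held on Day 8.

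This is a stated rule that gives a wrong by-visit result, not a missing detail, but it is minor. The summaries concerned are descriptive, no systematic testing between groups is planned, and the primary endpoint is not involved. The conclusion assumes that the general closest-to-target rule governs vital signs, since SAP 2.4.5.4 gives no other rule for several records in one window.

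**What to change.** Either of two edits to SAP 2.5.4.2.2 would do, made before database lock.

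- **Use the eCRF visit through Visit 9 and start the windows at Day 10.** This extends the rule already in force below Day 4 and keeps each scheduled visit under its own name. It is the simpler choice.
- **Split the row.** Set Hour 96 = 4 to <5 days, Hour 144 = 5 to <7 days and Hour 168 = 7 to <9 days. Days 4, 6 and 7 then each have their own time point, and Day 10 onward is unchanged. This means two added rows and one edited row, because Hour 168 must be narrowed to avoid overlap. The small drawback is that a Visit 9 held a day early would be labelled Hour 144, and a Visit 8 held a day late would fall in Hour 168.

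If one record for Days 4 to 8 is what the sponsor wants, the SAP should say so and the list of time points in SAP 2.4.5.4 should be amended to match. None of these changes needs new data.

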2.5.4.2.3 Time windows for ECG evaluation

Visit	Time window for the ECG assessment timing ^a
Baseline	Before IP start
Hour 2	After IP end to less than 3 hours
Hour 4	3 hours to less than 5 hours
Hour 6	5 hours to less than 7 hours
Hour 8	7 hours to less than 10 hours
Hour 12	10 hours to less than 18 hours
Hour 24	18 hours to less than 36 hours
Hour 48 (Day 2)	36 hours to less than 48 hours
Hour 72 (Day 3)	48 hours to less than 84 hours
Hour 96 (Day 4)	84 hours to less than 5 days
Hour 168 (Day 7)	5 days to less than 9 days

a: using the date and time of the first record from the triplicate ECG.

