2.1.5.5 ECG variables

A 12-lead ECG recording on Visit 2 (Day 0 hour 0, 2, 4, 6, 8, 12), Visit 3 (Day 1 hour 24), Visit 4 (Day 2 hour 48), Visit 5 (Day 3 hour 72) only if patient still hospitalized, Visit 6 (Day 4 hour 96) only if patient still hospitalized and Visit 9 (Day 7 hour 96), using a 12-lead ECG to extract triplicate measurements at each theoretical time point (each replicate record will be centrally read by a Core Lab Banook group (semi-automatic reading). The parameters that will be received from the ECG reading center are: RR, QT, QTcF, QTcB, PR and QRS (msec) and heart rate (bpm), but also ST deviation, T-wave morphology, U wave presence or absence.

All ECGs (triplicate) will be manually read by independent experts (except Visit 1 (Screen) for which automatic reading will be done).

For all quantitative ECG parameters, the mean of triplicate ECGs at each time point will be used for all analyses including PCSA analyses. As far as at least one record is available from a triplicate, it will be used in the mean calculations for analyses. No time restriction is applied for calculation of mean values from triplicate ECGs performed at the same visit.

For each set of triplicate ECGs, the associated date and time of the assessment is taken as the date and time of the first record of the triplicate.

The value to be used as baseline will be defined as the average of the triplicate assessments done on Day 0 T0 or the last available time point prior to first dosing for each treatment group.

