2.4.6.3 Concentration/ECG analyses

All the analyses will be performed on the PK/PD Safety population.

Endpoints

The Concentration-ECG analyses will be based on 12-lead ECG method.

The ECG parameters will include heart rate, QTcB, QTcF, PR and QRS intervals, corresponding to the change from baseline value. All post-dose assessments on Visit 2 (Day 0 hour 2, 4, 6, 8 and 12), Visit 3 (Day 1 hour 24), and Visit 4 (Day 2 hour 48) will be included, except Visit 5 (Day 3 hour 72), Visit 6 (Day 4 hour 96) and Visit 9 (Day 7 hour 168).

The pharmacokinetic endpoint will be the PK concentration of SSR97193, its active metabolite SSR97213 and OZ439 compounds. Post-dose concentrations below the lower limit of quantification (LLOQ) will be imputed to LLOQ / 2. LLOQ is defined as 5 ng/mL for FQ and SSR97213, 1 ng/mL for OZ439.

Relationships between concentrations (FQ, SSR97213 and OZ439) and change from baseline in ECG parameters will be analyzed into two ways:

- by combining the two compounds FQ and SSR97213 using the molecular weight (MW) 433.77 g.mol-1 for ferroquine and 419.74 g.mol-1 for SSR97213, in order to obtain an “total” concentration, separately from OZ439 (molecular weight of 469.28 g.mol-1)
- by using ferroquine, SSR97213 blood drug concentrations and OZ439 plasma concentrations as covariates in the same model

The relationship will be explored using data from OZ439/FQ on the restricted time window [Day 0, hour 2 – Day 2 hour 48]. Prediction of changes in ECG parameters (with 90% CI) will be obtained for each compound entering the models at each dose $C_{max,}$.

Exploratory plots

The relationship between change from baseline in ECG parameters and FQ (respectively SSR97213, OZ439) concentrations will be first explored graphically, in order to investigate any

potential delayed or sustained effects and the type of modeling to be done, using the following plots, by treatment group:

- Plot of mean (\pm SEM) change from baseline in ECG data and mean FQ (respectively SSR97213, OZ439) concentration versus time (hours post-dose) overlaid onto the same plot
- Hysteresis plot of mean change from baseline in ECG data and mean FQ (respectively SSR97213, OZ439) concentrations
- Histogram of distribution of time of largest change from baseline in HR, PR, QRS, QTcB and QTcF and largest FQ (respectively SSR97213 and OZ439) concentrations, respectively;

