2.5.5 Unscheduled visits

Unscheduled visit measurements will be used for computation of baseline and PCSAs. All visits will be re-allocated, and re-allocated visits measurements will be included in the by-visit summaries.

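### The SAP's laboratory and ECG windows place the 48 h target in the Hour 72 window, and the two columns of efficacy Table 4 disagree for Days 10, 14 and 21

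*SAP*

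**What the plan says.** **Laboratory and ECG windows.** SAP Section 2.5.4.2.3 (ECG) defines Hour 48 as "36 hours to less than 48 hours". Section 2.5.4.2.1 (laboratory) prints the same Hour 48 window, and both tables give Hour 72 as "48 hours to less than 84 hours". The neighbouring ECG row, Hour 24, is "18 hours to less than 36 hours".

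**How the windows are applied.** Section 2.5.4 assigns time points by the actual timing of an assessment, not by the visit it was recorded under. Where several values share a window, "only the assessment closest to the targeted time point will be used". Section 2.5.5 re-allocates all visits and adds that "re-allocated visits measurements will be included in the by-visit summaries".

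**Who is assessed when.** The schedule of activities has laboratory tests and an ECG at 48 h for every patient. The next assessment is conditional: "Visit 5 (Day 3 hour 72) only if patient still hospitalized" (Section 2.1.5.5; Section 2.1.5.3 has the same condition for laboratory tests).

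**Blood films.** Table 3 (Section 2.5.4.1) gives Hour 48 a window centred on its target, "45 hours to 51 hours". Table 4, which applies from Day 4, has one column of tolerances marked as inclusive (±1 day for Days 10 and 14, ±2 days for Days 21 and 28) and a second column of windows. For Days 10, 14 and 21 the second column does not follow from the first.

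**The concern.** A window should contain its own target. As printed, a laboratory sample or ECG at 48 h 10 min cannot be reported as Hour 48. In a discharged patient it becomes that patient's Hour 72 value. In a patient still in hospital it competes with the 72 h value, loses, and leaves Hour 48 empty.

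The Hour 48 row of each by-visit table would then hold only early assessments. The Hour 72 row would mix 48 h values from discharged patients with 72 h values from inpatients. Patients are kept in beyond 48 h when symptoms or parasitemia persist, so the mixture combines two times and two kinds of patient. Liver enzyme elevation and QTcF prolongation are the risks the protocol identifies in its benefit/risk section, and these tables describe their time course.

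In Table 4 a programmer cannot satisfy both columns. The choice decides which films count as out of window and so fall under the missing-count rules of Section 2.1.4.

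**Working it through.** **1. Does each target fall in its own window?** Read each row as a half-open interval. Of the ten post-dose ECG targets (2, 4, 6, 8, 12, 24, 48, 72, 96 and 168 h), nine fall in their own window. Of the seven laboratory targets (48, 72, 96 and 168 h; Days 14, 21 and 28), six do. The exception in both tables is 48 h, since 48 is not below 48 but does satisfy 48 ≤ 48 < 84.

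**2. Is the 48 h cut a choice or a slip?** Compare each printed ECG cut with the midpoint of the adjacent targets, (a + b)/2:

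| Targets (h) | Midpoint (h) | Printed cut (h) |
|---|---|---|
| 2, 4 | 3 | 3 |
| 4, 6 | 5 | 5 |
| 6, 8 | 7 | 7 |
| 8, 12 | 10 | 10 |
| 12, 24 | 18 | 18 |
| 24, 48 | 36 | 36 |
| 48, 72 | 60 | **48** |
| 72, 96 | 84 | 84 |

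Seven of eight match. The exception is the cut that excludes a target.

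**3. What happens to example records** (same result for laboratory tests and ECG):

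- 47.9 h only: Hour 48.
- 48.0 h or 48.5 h only: Hour 72.
- 48.0 h and 72.0 h: both fall in Hour 72. The 72.0 h value is used, the 48.0 h value is dropped, and Hour 48 is empty.
- 47.5 h and 72.0 h: both are labelled correctly.

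**4. How many records?** The documents do not give actual timings, so this is an assumption. Let T be normal with mean 48 + m and SD s (hours). The affected share is P(T ≥ 48) = Φ(m/s). Patient counts assume that all 140 randomized patients are dosed and assessed.

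| m (h) | s (h) | Share at or after 48 h | Of 140 |
|---|---|---|---|
| −1 | 0.5 | 0.023 | 3 |
| −1 | 1 | 0.159 | 22 |
| 0 | any | 0.500 | 70 |
| +1 | 1 | 0.841 | 118 |
| +1 | 0.5 | 0.977 | 137 |

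With a 60 h cut, the m = +1, s = 1 row (the worst in the table with a stated SD) needs a deviation of (60 − 49)/1 = 11 SD, so the share is effectively zero. On the SAP's own scale for films, (51 − 48)/(51 − 45) = 50% of the Hour 48 film window lies in what the safety tables call Hour 72. If only a date is held for a laboratory sample, Day 2 counts as 2 days, or 48 h, and every such sample goes to Hour 72. The SAP does not say whether laboratory times are collected.

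**5. Table 4 in whole days:**

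| Target | From stated tolerance | From printed window | Lost | Gained |
|---|---|---|---|---|
| Day 10 | 9–11 | 9–10 | 11 | none |
| Day 14 | 13–15 | 12–14 | 15 | 12 |
| Day 21 | 19–23 | 19–22 | 23 | none |
| Day 28 | 26–30 | 26–30 | none | none |

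All eight rows of Table 3 agree with their tolerances. The protocol schedule allows Day 14 ± 1 and Day 21 ± 2, which matches Table 4's tolerance column.

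**The case against.** **The effect is narrow.** Safety analyses are descriptive. Abnormality counts use every on-treatment evaluation (Section 2.4.5), the QTc outlier listing uses all post-dose times (Section 2.4.5.5), and worst values, the ALT/bilirubin peak plot and the Hy's law listing do not depend on windows. Vital signs before Day 4 use the recorded visit. All of this stands, and it limits the size of the point. It does not repair the by-visit tables.

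**The 60 h cut is inferred.** Midpoints are not a stated rule: the ECG cut between 96 h and 168 h is 120 h, not 132 h, and the later laboratory cuts are not exact midpoints. That is correct, and any cut clearly after 48 h would cure the defect. Of the candidates, 60 h fits the surrounding rows.

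**The concentration–ECG analysis may not be touched.** Section 2.4.6.3 names its inclusions by visit, with Visit 4 in and Visit 5 out. Protocol Table 3 has no 48 h sample for FQ or SSR97213, so the models as written lack a covariate at 48 h whichever window holds the ECG. This largely stands. The section also sets a time limit ending at hour 48 without saying whether visit or actual time governs, so only a request for clarity remains.

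**Table 4 might count elapsed days.** On that reading, 9 to <11 and 19 to <23 reproduce ±1 and ±2 except at the exact upper end. Against it, the text above the table places assessments by actual day, and the zero-tolerance rows for Days 4 to 7 make sense only in whole days. The Day 14 lower bound of 12 contradicts ±1 on either reading.

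**Conclusion.** The concern holds. As printed, both safety tables exclude the 48 h target from its own window, and no other section of the SAP overrides this. By-visit laboratory and ECG summaries at Hours 48 and 72 would be mislabelled for every assessment made at or after 48.0 h. That share is unknown: about 2% to 98% under the assumed timings, 50% if timing is symmetric about target, and near zero only if almost all assessments are early. Outlier, worst-value and abnormality analyses are unaffected.

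Table 4 contradicts itself in three rows. On whole-day counting, Days 11, 15 and 23 fall in no window and Day 12 is admitted. The Day 28 row used for the primary endpoint is correct. The imputation rules, the any-day definition of late parasitological failure and the use of actual time for re-emergence outside the windows all limit the effect, so no changed ACPR outcome is claimed. This should be fixed, but it does not threaten the primary analysis.

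**What to change.** - **Sections 2.5.4.2.1 and 2.5.4.2.3:** set Hour 48 to 36 to <60 h and Hour 72 to 60 to <84 h. Every laboratory and ECG target then falls in its own window.
- **Table 4:** print Day 10 as Days 9–11, Day 14 as Days 13–15 and Day 21 as Days 19–23, all inclusive, and say that days are whole days from dosing. If a wider Day 14 window reaching back to Day 12 was intended, change the tolerance column instead and say so.
- **Section 2.4.6.3 (optional clarification):** state whether the Hour 48 ECG is included by recorded visit or by the corrected window, and word the upper time limit so that an ECG shortly after 48 h is kept.

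The cost is a few SAP table cells and one or two sentences. No new data and no protocol change are needed.
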